- after treatment of the first 10 subjects (5 in the TH arm and 5 in the control arm)
- at the conclusion of the study

In addition, the DSMB may convene additional meetings if necessary to ensure the ongoing monitoring and safety of the subjects treated with therapeutic hypothermia (TH). A copy of the DSMB charter is located in Appendix 2.

We will collect all treatment emergent and serious unsolicited adverse events during the index hospitalization. A treatment emergent adverse event is any untoward medical occurrence associated with the use of therapeutic hypothermia, whether or not considered related. The DSMB will be informed of expected adverse events, such as shivering, bleeding, and bradycardia, that result in termination of the protocol. Additionally, any unexpected adverse events while undergoing TH will be reported to the DSMB, whether deemed related to TH or not. All adverse event details will be provided to the DSMB prior to the meeting with ample time allowed for analysis. This will include details of the individual adverse events as well as the PI's analysis related to causality, severity and frequency. The DSMB will be responsible for

confirmation of the PI's assessment of all adverse events and final adjudication of all adverse events.

The DSMB will include the following individuals who have agreed to serve on it:

- [name] (University of Chicago Medicine – Section of Cardiology)
- [name] (Inova Health System – Section of Cardiology)
- [name] (University of Chicago Medicine – Section of Cardiology)

Payment to Subjects

Participants will not receive monetary compensation for their participation in this study. The cost of the TH catheters, thermal regulation system and associated monitoring will be part of the study costs and patients will not be charged for these services.

Informed Consent

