Appendix 2 – DSMB Charter

1. Introduction

This Charter is for the Data and Safety Monitoring Board (DSMB) for Cardiogenic Shock Intravascular Cooling Trial (CHILL-SHOCK). The DSMB will consist of a team of clinical researchers who are unaffiliated with this project. The members of the DSMB will not be investigators in this study and will be experienced in conducting and interpreting clinical trials. Their responsibilities will include reviewing the efficacy and safety endpoints at the set times points, as stated below. The Charter is intended to be a living document. The DSMB may wish to review it at regular intervals to determine whether any changes in the procedure are necessary.

2. Responsibilities of the DSMB

The DSMB is responsible for safeguarding the interests of study participants, assessing the safety and efficacy of study procedures, and for monitoring the overall conduct of the study.

The DSMB is an independent group advisory to the study PI and is required to provide recommendations about starting, continuing, and stopping the study. In addition, the DSMB is asked to make recommendations, as appropriate, to/about:

- Selection, recruitment, and retention of participants
- Adherence to protocol requirements
- Completeness, quality, and analysis of measurements
- Amendments to the study protocol and consent forms
- Confirmation of the PI's assessment of adverse events
- Final adjudication of all adverse events, as defined by *Table A* below
- Participant safety
- Notification of and referral for abnormal findings

3. DSMB Members

DSMB Chair: [name] University of Chicago Medicine Department of Medicine Section of Cardiology Assistant Professor of Medicine	[name], MSc Inova Health System Department of Medicine Section of Cardiology Professor of Medicine	[name] University of Chicago Medicine Department of Medicine Section of Cardiology Assistant Professor of Medicine
---------------------------------------------------------------------------------------------------------------------------------------------------------------------------	-----------------------------------------------------------------------------------------------------------------------------------------------	---------------------------------------------------------------------------------------------------------------------------------------------------

4. Scheduling, Timing, and Organization of Meetings: Data and Safety Monitoring Meetings

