The DSMB will meet (in person or via telephone conference) a minimum of 3 times:

- after treatment of the first 4 subjects (2 in the TH arm and 2 in the control arm)
- after treatment of the first 10 subjects (5 in the TH arm and 5 in the control arm)
- at the conclusion of the study

The DSMB may convene additional meetings if necessary to ensure the ongoing monitoring and safety of the subjects treated with TH.

A quorum of at least two (2) DSMB members needs to be present for a meeting to commence. Members may either be present in person or have the option to phone-in if unable to arrive at the meeting location.

All DSMB members will receive an agenda prior to the meeting. In the event that a DSMB member is unable to attend a meeting, that member will receive minutes, as well as any additional notes, with the opportunity to share any additional thoughts on the distributed information.

5. Grading and Attribution Methods for Adverse Events

Grading Scale

The DSMB and the study team will utilize the Adverse Event Grading Scale provided in Table A. All adverse events will be graded according to this scale, the PI will prepare data regarding adverse events for review by the DSMB prior to meeting, and any additional details will be provided to the DSMB by the PI, as necessary.

Table A – Safety Reporting Definitions

Term	Definition
Adverse Event (AE) Ref: ISO 14155-2011 Ref: MEDDEV 2.7/3 12/2010	
Any untoward medical occurrence, unintended disease or injury, or any untoward clinical signs (including an abnormal laboratory finding) in subjects, users or other persons, whether or not related to the investigational medical device.
 
This definition includes events related to the procedures involved (any procedure in the clinical investigation plan).

Adverse Device Effect (ADE) Ref: ISO 14155-2011 Ref: MEDDEV 2.7/3 12/2010	
Adverse event related to the use of an investigational medical device
 
NOTE 1: This definition includes any adverse event resulting from insufficient or inadequate instructions for use, the deployment, the implantation, the installation, the operation, or any malfunction of the investigational medical device.
 
NOTE 2: This definition includes any event resulting from use error or from intentional misuse of the investigational medical device.

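### The treatment-emergent definition leaves non-serious adverse events in control patients without a collection rule, in conflict with Table A and Appendix 1

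*Combined protocol and SAP*

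**What the plan says.** The collection rule is in the protocol's Data Safety Monitoring Board section: "We will collect all treatment emergent and serious unsolicited adverse events during the index hospitalization". The next sentence defines the first of the two categories: "A treatment emergent adverse event is any untoward medical occurrence associated with the use of therapeutic hypothermia, whether or not considered related".

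The same paragraph names two notifications to the DSMB. One is for "expected adverse events, such as shivering, bleeding, and bradycardia, that result in termination of the protocol". The other is that "any unexpected adverse events while undergoing TH will be reported to the DSMB, whether deemed related to TH or not". It then adds a general sentence: "All adverse event details will be provided to the DSMB prior to the meeting with ample time allowed for analysis".

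The DSMB charter (Appendix 2) is wider. Table A defines an adverse event as any untoward occurrence "in subjects, users or other persons, whether or not related to the investigational medical device". The charter's introduction gives the board the task of "reviewing the efficacy and safety endpoints at the set times points", and a later section has it look at adverse event and other safety data at every meeting.

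Appendix 1 has an adverse event row at 18-24 hours, 48-96 hours, 30 days and 90 days. That row has no arm limit. The potassium and glucose rows are limited to patients randomized to cooling.

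**The concern.** The trial's stated purpose is to assess the safety of TH by randomizing patients to TH or to standard care alone. Arrhythmia, bleeding and high glucose can arise in cardiogenic shock without cooling, so TH events mean little without the control rate beside them. If site staff follow the DSMB section, non-serious events are recorded in cooled patients and not in controls. The adverse event table then shows an excess produced by the definition. The board, which confirms the investigator's assessments and makes the final adjudication, would lack a proper background rate for those events.

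The same one-sidedness appears under Mitigating Risks associated with TH. Hypokalemia below 3.0 mEq/L counts there as an adverse event only in patients undergoing TH, although the matching primary safety endpoint has no such limit. Hyperglycemia is recorded as an adverse event when it is attributed to TH.

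**Working it through.** The plan gives no adverse event rate, so there is no figure of its own to reproduce. The check compares the rules and then shows a scale under stated assumptions.

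**1. Who is covered, and when**

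| Source | Patients covered | Period |
|---|---|---|
| DSMB section, treatment-emergent events | those with use of TH | index hospitalization |
| DSMB section, serious unsolicited events | no arm limit | index hospitalization |
| Charter, Table A | any subject | none stated |
| Appendix 1, adverse event row | no arm limit | 18-24 h, 48-96 h, 30 days, 90 days |

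A non-serious control event meets neither category in the DSMB section, but it meets Table A and falls under the Appendix 1 row. The collection period also differs: the DSMB section ends at discharge and Appendix 1 runs to 90 days.

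**2. What the two notifications reach**

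- Expected events count if they end the protocol. The only protocol stops described under Mitigating Risks are stops of TH, so a control cannot trigger this notification.
- Unexpected events count while the patient is undergoing TH. On a plain reading this is the 24-hour cooling period.
- Procedures gives rewarming at 0.3°C per hour to 37°C. From 34°C this takes (37 − 34)/0.3 = 10 h. From 32°C it takes (37 − 32)/0.3 = 16.7 h. The risk section itself names glucose and potassium shifts during rewarming.

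**3. Scale, by assumption only**

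Take 10 patients per arm, the same true rate r of one event type in both arms, and a share c of control events recorded. The expected counts are 10r and 10rc, and the spurious risk difference is r(1 − c). With r = 40% and c = 0 this is 4/10 versus 0/10.

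With no control events recorded, the two-sided Fisher p-value for x TH events is 2·C(10,x)/C(20,x):

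- x = 4: 2 × 210/4,845 = 0.087
- x = 5: 2 × 252/15,504 = 0.0325

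So 4 versus 0 does not reach 0.05, and 5 versus 0 does. With c = 0, the chance of a false TH-worse result at 0.05 is P(X ≥ 5) for X ~ Bin(10, r). The other columns come from enumerating both binomials.

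| r | Expected TH events | c = 1 | c = 0.5 | c = 0 |
|---|---|---|---|---|
| 20% | 2 | 0.4% | 1.2% | 3.3% |
| 30% | 3 | 0.6% | 3.4% | 15.0% |
| 50% | 5 | 0.6% | 8.6% | 62.3% |

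These figures concern one line of an adverse event table. Statistical Methods names no test of treatment-emergent events, so the practical harm is a misleading description more than a false p-value.

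**The case against.** A reader might infer that control-arm and post-cooling harms fall outside the safety comparison altogether, or that the DSMB sees only events on TH. The documents do not support either reading.

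- The planned safety comparison is a between-arm test of the primary safety endpoints, which does not use the treatment-emergent definition. The arrhythmia and infection endpoints are worded for either arm, as is in-hospital mortality. The bleeding endpoint is tied to the cooling catheter or resulting coagulopathy, but by its own wording, which is a separate matter.
- Serious unsolicited events are collected without an arm limit.
- Events after cooling are collected. The window is the whole index hospitalization, and Appendix 1 adds later assessments.
- All event details go to the board before each meeting, and the charter has it review adverse event data each time. The two TH-tied sentences can be read as extra notifications on top of that package.

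All of this stands, and it limits the point. It does not remove it, because the board can review only what was collected, and the DSMB section gives no rule for collecting non-serious control events. Staff who work from Table A and Appendix 1 would record them, so the bias depends on which text is followed. The 40% rate and the zero capture are assumptions.

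**Conclusion.** The collection rule is wrong as written, with moderate weight. A stated definition, not a missing detail, excludes non-serious control events, and it contradicts Table A and the Appendix 1 row.

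If that definition is followed, the descriptive adverse event table and the DSMB's background rate for non-serious events are biased against TH. For assumed equal true rates of 20% to 50% and no control capture, the expected display is 2 to 5 of 10 versus 0 of 10. If half of the control events are captured, it is 2 to 5 versus 1 to 2.5. If Table A is followed, this bias does not arise.

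The second part is narrower. The two event-specific notifications do not cover control events and, on a plain reading, do not cover the 10 to 17 hours of rewarming or later. This bears on notice between meetings, since the full details still reach the board before each scheduled one.

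**What to change.** 1. Replace the treatment-emergent definition in the DSMB section with: *any Table A adverse event with onset or worsening after randomization, in either arm*.
2. Apply the unexpected-event notification to both arms over the whole collection window.
3. Have the DSMB package tabulate all adverse events by arm on the same clock, counted from randomization, whether or not TH was stopped.
4. State one collection window, and reconcile the index hospitalization with the 30- and 90-day adverse event visits in Appendix 1.
5. Apply the hypokalemia and hyperglycemia recording rules under Mitigating Risks to both arms. Report the cooled-only potassium and glucose checks in Appendix 1 as a source of unequal detection. This concerns recording and reporting only.

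The cost is protocol wording, adverse event recording in about 10 controls for whom Appendix 1 already schedules assessments, and a longer listing for the DSMB.

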Laboratory, echocardiographic, and hemodynamic parameters will be obtained for patients prior to randomization, near the end of 24 hour cooling therapy, and after 48-96 hours post-randomization. Core temperature will be measured via either thermal tip at the end of a transurethral urinary catheter or endotracheal temperature probe in intubated patients. Rewarming will be accomplished at 0.3°C per hour until temperature reaches 37°C.

Target Enrollment and Study Duration

In this initial pilot study, we anticipate enrolling 20 patients to the study, 10 randomized to standard medical therapy and 10 patients randomized to standard medical therapy and 24 hours of TH. We anticipate completing enrollment within 6 months.

Statistical Methods

The three-dichotomous primary endpoints will be analyzed using a two-sample independent proportion test or a Fisher's exact test with a Bonferroni method continuity correction for multiple endpoints. Furthermore, numerical secondary endpoints will be presented as either

mean \pm standard deviation or median (interquartile range) based upon the distribution of the data. In addition, all numerical secondary endpoints will be assessed using two independent t tests or Mann-Whitney U test for comparisons. Categorical variables will be tested with chi-square tests of association or Fisher's exact tests. Differences will be considered significant using an alpha value of 0.05 for a two-sided test. Analyses will be performed using STATA MP Version 14 (College Station, TX).

Potential risks and benefits to subjects

A. Benefits:

There is mounting evidence that TH has positive effects on cardiac function. Multiple studies have suggested that TH may offer particular benefit in cardiogenic shock. In this prospective trial, the patients will be randomized to TH or standard medical care using simple randomization. With TH, we expect increased cardiac output, increased contractility, lower SVR, and higher cardiac power index which will lead to improved hemodynamics and potentially decreasing pressor requirements.

B. Risks:

Anticipated adverse events that could possibly occur during the study include, but are not limited to:

1. *Risks associated with TH*
 - a. Shivering
 - b. Arrhythmia
 - c. Coagulopathy with or without clinically significant bleeding
 - d. Hyperglycemia
 - e. Hypothermia
 - f. Electrolyte abnormalities
 - g. Infections
2. *Risks associated with cooling catheter insertion*
 - a. Bleeding
 - b. Infection

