In addition to bradycardia, ventricular arrhythmias are potential adverse effects of TH. While ventricular arrhythmias have been reported with TH, data from trials suggests that there is no demonstrable increase in risk of ventricular arrhythmias in patients undergoing therapeutic hypothermia.^{24,25} Importantly, patients in cardiogenic shock have a high risk of developing ventricular arrhythmias either due to ischemia or underlying myocardial scarring. All ventricular arrhythmia episodes requiring intervention will be recorded. If arrhythmia is deemed to be as a result of hypothermia and alternative explanations have been exhausted, the patient will be rewarming to normothermia per the rewarming protocol.

Another risk associated with TH is mild coagulopathy. Temperatures below 33°C have been associated with mild platelet dysfunction in vitro. However, the risk of bleeding with mild TH (32-34°C) is minimal and none of the trials of TH in cardiac arrest or stroke have demonstrated increased risk of bleeding.^{20,21} TH has also been used safely in patients with ischemic stroke who are treated with tPA.²² Based on the currently published data, the risk of bleeding with TH is minimal. Bleeding adverse events will be classified using the GUSTO bleeding criteria.²⁶ In patients who develop moderate bleeding deemed to be a direct result of TH, initial conservative measures of simple transfusions will be implemented. However, if bleeding does not respond to these conservative measures or progresses to severe bleeding, the TH protocol will be stopped and patients will be safely rewarmed.

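### A serious or treated ventricular arrhythmia that does not end cooling need not reach the DSMB between the subject-10 meeting and study end

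*Combined protocol and SAP*

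**What the plan says.** Section D, Data Safety Monitoring Board, plans at least three meetings. The first follows 4 subjects, the second comes "after treatment of the first 10 subjects (5 in the TH arm and 5 in the control arm", and the third is at study end. The board may call more.

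The same section gives three ways for an adverse event to reach the board:

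- **Expected events:** "The DSMB will be informed of expected adverse events, such as shivering, bleeding, and bradycardia, that result in termination of the protocol".
- **Unexpected events:** "any unexpected adverse events while undergoing TH will be reported to the DSMB, whether deemed related to TH or not".
- **Meeting packet:** "All adverse event details will be provided to the DSMB prior to the meeting with ample time allowed for analysis".

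Neither of the first two carries a deadline, and the third is tied to a meeting.

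On ventricular arrhythmia, section B (Risks) puts arrhythmia on a list introduced by "Anticipated adverse events that could possibly occur during the study include, but are not limited to". Mitigating Risks associated with TH adds that "ventricular arrhythmias are potential adverse effects of TH", but also that trial data suggest "there is no demonstrable increase in risk of ventricular arrhythmias in patients undergoing therapeutic hypothermia". Treated episodes are recorded. Rewarming follows "If arrhythmia is deemed to be as a result of hypothermia and alternative explanations have been exhausted".

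In the DSMB charter (Appendix 2), sections 5 and 6 have adverse event data prepared before, and reviewed at, each meeting. Table C sets reporting to FDA and IRB and has no DSMB column.

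**The concern.** Establishing the safety of cooling is the stated objective of this pilot. A ventricular arrhythmia that needs medical therapy counts towards primary safety endpoint 1. The charter makes the DSMB responsible for advising whether to continue or stop.

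The expected-event rule ties notice to whether cooling was stopped, and not to how serious the event was or whether it was judged related. An important event can therefore fall outside the notice because the treating team kept cooling. The decision at stake is whether the board calls an extra meeting before more patients are cooled. It can do so only if it knows of the event.

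**Working it through.** The plan gives no arrhythmia rate and no calculation on this point, so there is no figure to reproduce. The check has three parts.

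**1. Routes to the board for a ventricular arrhythmia treated during TH, cooling continued, after the subject-10 meeting**

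| Route | Does it reach the DSMB before study end? |
|---|---|
| Expected-event notice (section D) | No, because the protocol was not ended |
| Unexpected-event notice (section D) | Only if classed as unexpected, and then with no deadline |
| Meeting packet (section D; charter sections 5 and 6) | Only if an extra meeting is called |
| Serious-event row (Table C) | Goes to FDA within 48 hours and to the IRB at annual review; no DSMB entry |
| Unanticipated-device-effect row (Table C) | Goes to FDA and IRB, with a possible halt; no DSMB entry |

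The label is not fully settled. The anticipated list and the sentence naming ventricular arrhythmia as a potential effect point to expected. The statement about no demonstrable increase in risk leaves room for unexpected. The expected label is the more natural one.

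Continued cooling is realistic. The rewarming condition needs attribution to hypothermia with alternatives exhausted, and the same paragraph names ischemia and scar as common causes in these patients. Table B classes an event as Related when another cause is equally likely. An event can therefore be Related without meeting the rewarming condition.

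**2. Patients exposed and chance of an event**

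Inputs from the documents are 20 planned subjects, 10 of them on TH, and a second meeting after 10 subjects (5 on TH). That leaves 20 − 10 = 10 subjects, of whom 10 − 5 = 5 are planned for TH.

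Two inputs are assumptions: a treated ventricular arrhythmia in p = 10%, 20% or 30% of TH patients, and cooling continued in half of those. The rate of interest is then q = p/2.

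- P(at least one in 5) = 1 − (1 − q)^5
- q = 5%: 1 − 0.95^5 = 0.226
- q = 10%: 1 − 0.90^5 = 0.410
- q = 15%: 1 − 0.85^5 = 0.556

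Allocation is by simple randomization, so exactly 5 of the last 10 on TH has probability 252/1024 = 0.246. Letting each of the 10 be on TH with probability 1/2 gives 1 − (1 − q/2)^10 = 0.224, 0.401 and 0.541. The range hardly moves.

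**3. Length of the wait**

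Enrollment is expected within 6 months. With even accrual the spacing is 6/20 = 0.3 months, and an event in subject k waits 0.3 × (20 − k) months until subject 20 is enrolled.

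- Longest (subject 11): 0.3 × 9 = 2.7 months
- Average over subjects 11 to 20: 0.3 × 4.5 = 1.35, about 1.4 months

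Appendix 1 schedules a 90-day follow-up. If study end includes it, add 90/30.4 = 3.0 months, giving about 4.3 on average and 5.7 at most.

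**The case against.** The best defence is that nothing is lost. Every adverse event goes to the board with the investigator's view of causality and severity, and the board makes the final adjudication. Serious events reach FDA within 48 hours. The board may convene at any time, and its charter is open to revision, so it could write its own notice rule after subject 4 or subject 10. An arrhythmia firmly blamed on hypothermia leads to rewarming, which ends cooling and triggers the notice. What remains is mostly arrhythmia attributed to ischemia or scar, which says less about cooling. The Background also reports no severe adverse events in 14 prospectively cooled shock patients, so high assumed rates may be generous.

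Most of this stands, and it limits the point to timing. It does not close the gap, because the power to meet or to amend a charter does not tell the board that an event has happened. Attribution to ischemia or scar by the treating team is also a judgment the board is there to check.

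Two stronger readings are tempting. A reader might infer that such arrhythmias are kept from the DSMB altogether; the meeting packet and final adjudication contradict that. A reader might also take the chance of any treated ventricular arrhythmia among 5 patients (41% to 83% at rates of 10% to 30%) as the size of the gap. That would count events that end cooling, which must be notified.

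**Conclusion.** The point holds as a gap in timing. No rule requires that the board be told, between the subject-10 meeting and study end, of a serious or treated ventricular arrhythmia during TH with cooling continued. That window covers about half the planned TH patients.

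The 23% to 56% chance of at least one such event rests on two assumptions that the documents neither give nor contradict: the 10% to 30% arrhythmia rate and continuation in half. It is the chance that an event occurs which the rule could leave un-notified, not the chance that the investigator would stay silent. The waits rest on even accrual and on no extra meeting being called. No endpoint, analysis or final safety conclusion changes. This is a worthwhile improvement of modest priority.

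**What to change.** Amend section D and Table C (adding a DSMB column) to state that the following are copied to the DSMB within 48 hours of the investigator learning of them, whether or not cooling was stopped, with the Table B class:

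- any serious adverse event or serious adverse device effect in a TH patient;
- any ventricular arrhythmia requiring intervention during TH.

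Control-arm serious events and non-serious events, including other treated arrhythmias, can stay in the meeting packet, with control-arm data supplied if the board asks. The rewarming threshold is a separate clinical choice and need not change.

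The cost is a wording amendment and no new procedures. At the assumed rates, arrhythmia notices would concern about 10 × 0.10 = 1 to 10 × 0.30 = 3 of the 10 planned TH patients. Serious-event notices will be more numerous. At the 50% upper mortality figure in the Background (given for infarct-related shock), deaths alone could reach 10 × 0.50 = 5 on TH, and Table A's definition of serious is broad. Some notices will be background events of shock. The serious-event reports are already prepared for FDA on the same 48-hour clock, so for those the board simply receives a copy.
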